## **9.3 Case Report Forms (as applicable)**

Case report forms will be developed by the study coordinator and include forms for collecting information on demographics, medical history, concurrent meds., AEs, protocol deviations, medication compliance, laboratory results, disease status, vital signs and quality of life. All data requested on the CRF will be recorded. All missing data will be explained. If a space on the CRF is left blank because the procedure was not done or the question was not asked, we will write "N/D". If the item is not applicable to the individual case, we will write "N/A". All entries will be printed legibly in black ink. If any entry error has been made we will draw a single straight line through the incorrect entry and enter the correct data above it. All such changes will be initialed and dated. We will not white out or erase errors. For clarification of illegible or uncertain entries, we will print the clarification above the item, then initial and date it.

## **9.4 Records Retention**

We will retain study essential documents for 2 years after the completion of the study.

# **10 Study Monitoring, Auditing, and Inspecting**

## **10.1 Study Monitoring Plan**

This study will follow the monitoring plan established by the UNC TraCS DSMB.

## **10.2 Auditing and Inspecting**

We will permit study-related monitoring, audits, and inspections by the IRB, the sponsor, government regulatory bodies, and University compliance and quality assurance groups of all study related documents (e.g. source documents, regulatory documents, data collection instruments, study data etc.). The investigator will ensure the capability for inspections of applicable study-related facilities (e.g. pharmacy, diagnostic laboratory, etc.).

## **11 Ethical Considerations**

This study is a proof of concept study testing the hypothesis that patients in complete remission after induction therapy, and with recovery of B cells with a normalization of CD5+ B cells may avoid exposure to maintenance immunosuppression. The randomization in this study may be justified by the following considerations:

- 1) There is clinical precedence to following patients treated with induction therapy with rituximab and corticosteroids without additional maintenance therapy. In the landmark study of induction therapy with corticosteroids in combination with rituximab vs cyclophosphamide x 3 months followed by azathioprine maintenance therapy, patients assigned to the rituximab group did NOT receive any additional maintenance therapy after the initial four weekly doses of rituximab. (Stone JH 2010).
- 2) In this randomized controlled trial, induction therapy with rituximab and NO maintenance therapy was not associated with a statistically significantly different rate of relapse, and a statistically significantly LOWER rate of adverse events. While the latter results cannot be directly attributable to the avoidance of maintenance immunotherapy, it raises the possibility that such avoidance may in fact be associated with a decreased risk of infectious complications.
- 3) Patients will be followed carefully with frequent clinic visits to detect any early signs of relapse. Any sign of relapse will result in exiting the patient from the investigational part of the study and instituting immunotherapy at the decision of the treating nephrologist.

This study will be conducted according to US and international standards of Good Clinical Practice (FDA Title 21 part 312 and International Conference on Harmonization guidelines), applicable government regulations and Institutional research policies and procedures.

This protocol and any amendments will be submitted to a properly constituted independent Ethics Committee (EC) or Institutional Review Board (IRB), in agreement with local legal prescriptions, for formal approval of the study conduct. The decision of the EC/IRB concerning the conduct of the study will be made in writing to the investigator and a copy of this decision will be provided to the sponsor before commencement of this study. The investigator should provide a list of EC/IRB members and their affiliate to the sponsor.

All subjects for this study will be provided a consent form describing this study and providing sufficient information for subjects to make an informed decision about their participation in this study. See **Appendix B** for a copy of the Subject Informed Consent Form. This consent form will be submitted with the protocol for review and approval by the EC/IRB for the study. The formal consent of a subject, using the EC/IRB-approved consent form, must be obtained before that subject undergoes any study procedure. The consent form must be signed by the subject or legally acceptable surrogate, and the investigator-designated research professional obtaining the consent.

## **12 Study Finances**

### **12.1 Funding Source**

National Institutes of Health

## **12.2 Conflict of Interest**

This study is supported by an NIDDK grant (P01-DK058335-16), with no additional support. There is not external support from industry. As such, we anticipate no conflict of interest from any investigator. All study personnel have completed the UNC conflict of interest attestation.

## **13 Publication Plan**

This study is conducted as a single center study at the UNC Kidney Center, under a grant from the NIDDK. The conduct of the trial, review of the data and its analysis will be performed by the co-investigators and research staff. No approval requirements from parties external to the research team are anticipated. Access to the publication and data will be in accordance to the general policies of the NIH and University of North Carolina.

We will plan to publish descriptive information and outcomes from the study. This will be done to make results available to the research community with the intent of informing but also with the potential for collaboration with other sites who see these patients for participation in a future trial. The publication may be in the form of a short report aimed at describing the ability of enrolling patients into this type of study and to show where data for sample size estimates will be drawn from.

    Appendix 1: Current members of the DSMB

Abbreviations

AE	Adverse event
DSMB	Data and Safety Monitoring Board, NC TraCS Institute
DSMC	Lineberger Data and Safety Monitoring Committee, PRC
CTRC	Clinical and Translational Research Center
IRB	UNC Biomedical Institutional Review Board
NIH	National Institutes of Health
PI	Principal Investigator
PRC	UNC Lineberger Oncology Protocol Review Committee
TraCS	North Carolina Translational and Clinical Sciences Institute
UNC	University of North Carolina at Chapel Hill

## Introduction

The North Carolina Translational and Clinical Sciences (TraCS) Institute is committed to the safety of patients participating in clinical trials at our institution. In addition, it is committed to data accuracy and protocol compliance. The NC TraCS Institute has established an institutional plan to provide data safety and monitoring for selected clinical trials conducted at UNC. This plan is designed to comply with policies and guidelines regarding data and safety monitoring from the National Institutes of Health (<http://grants.nih.gov/grants/guide/notice-files/not98-084.html>; <http://nih.gov/grants/guide/notice-files/NOT-OD-00-038.html>).

This charter is for the Data Safety and Monitoring Board (DSMB) of the North Carolina TraCS Institute. The charter contains the following:

- A description of the composition and organization of the DSMB
- Details the roles and responsibilities of DSMB members
- Outlines the responsibilities of the Principal Investigators and Sponsors
- Lists important contact persons

## Organization

### Overview

The DSMB functions as a committee within the NC TraCS Institute. The charge to the DSMB is review clinical trials to assure patient safety both by evaluating adverse events (AEs) and interim analyses of both safety and efficacy.

### Committee Structure

The DSMB Chair (currently [name]) has the overall responsibility for the chairing the DSMB committee and reporting its findings to the UNC Biomedical IRB. The Committee will be under the direct supervision of the NC TraCS Institute Director or designated representative. The Committee will consist of a chair, an ethicist, an epidemiologist, a biostatistician, and one or more clinical researchers. Committee members will serve for 3-year terms, but may be reappointed. Members will be appointed to the Committee by the Chair, Director or designated representative. A member of the DSMB can be removed due to poor attendance, inadequate demonstration of effort, unprofessional conduct and /or failure to act in accordance with the objectives of the DSMB. A list of current DSMB members can be found in Appendix 1.

## PROCESS

### Eligibility

A clinical trial is defined as “a prospective study involving human subjects designed to answer specific questions about the effects or impact of particular biomedical or behavior interventions; these may include drugs, treatments, devices, or behavior or nutritional strategies.” Studies that include nutritional, behavioral, and psychosocial interventions are considered to be clinical trials. Studies evaluating diagnostics (imaging, etc.) in which findings alter the patient’s clinical care are also considered to be clinical trials. Observational studies, epidemiologic studies, studies of diagnostics that do not affect patient care, and studies that do not test interventions are not considered to be clinical trials.

### DSMB Functions and Activities

The DSMB is responsible for reviewing data from clinical trials approved by the UNC Biomedical IRB. Investigators with commercially or governmentally sponsored trials will normally work with their sponsor’s DSMB.

The DSMB will review data from the following types of trials, when review is deemed necessary by the Biomedical IRB or requested by the Principal Investigator (PI), in order to ensure the safety of participating subjects.

- Phase I, I/II, II, and II/III trials when such review is deemed necessary by the UNC Biomedical Institutional Review Board and the Principal Investigator.
- Phase III clinical trials (single site trials where the PI is a UNC faculty member and for which UNC is the sponsor)
- Phase IV clinical trials (single site trials where the PI is a UNC faculty member and for which UNC is the sponsor)
- Select multicenter clinical trials in which UNC is the coordinating center or the PI of the study is a UNC faculty member IF the DSMB determines that it has adequate resources to conduct the monitoring required of the study.

**The DSMB will meet at least every other month and has the following responsibilities.**

- Assessing risk and complexity of clinical trials submitted for review
- Determining the appropriate level of data and safety monitoring
- Reviewing serious adverse events (AEs) reports when requested.
- Reviewing yearly data and safety monitoring reports when requested. Recommending appropriate actions (closure, increased monitoring, etc.) to the Principal Investigator, UNC Biomedical IRB, and the Director or designated representative.
- Communicating its finding with the Biomedical IRB
- Preparing minutes for all meetings
- Preparing an annual summary of activity for review by the Director, NC TraCS Institute
- Review of the monthly reports of the UNC Lineberger Oncology Protocol Review Committee (PRC) -Data and Safety Monitoring Subcommittee (DSMS)
- Assessing ethical and scientific soundness of trials reviewed

#### **DSMB-Investigator Communications**

The DSMB will make available to investigators the following:

- An Annual Data Reporting form for annual reporting of all AEs
- A Data Safety Monitoring Plan template

Principal Investigators shall make available to the DSMB the following information:

- A copy of the approval letter from the UNC Biomedical Institutional Review Board
- A Data Safety Monitoring Plan
- All adverse event reports using the most current UNC Biomedical Institutional Review Board form
- An annual summary of all AEs

## **Relation to Biomedical Institutional Review Board and Lineberger Oncology Protocol Review Committee**

The DSMB will report its findings and make recommendations to the UNC Biomedical IRB. For research conducted by the Lineberger Cancer Center, the DSMB will report its findings and make recommendations to the UNC Lineberger Oncology Protocol Review Committee (PRC). Trials required to have an independent data and safety monitoring board as defined in this charter are expected to use the NC TraCS Institute DSMB instead of establishing their own independent board, unless outside expertise not available on the DSMB is necessary to adequately monitor the trial.

Notice of a recommendation of early closure or suspension will be reported directly to the Biomedical IRB and the Director or designated representative. As appropriate, such recommendations will be reported to the Director of the Lineberger Cancer Center and the Director of the Clinical Translational Research Center. The Chair of the DSMB in conjunction with the Chair of the Biomedical IRB is responsible for seeing that these trials are closed to accrual.

### **Guidelines for Members**

In order for the DSMB to fulfill its responsibilities, the member will observe the following guidelines:

- Members are free of apparent conflicts of interest involving financial, scientific, or regulatory matters. In case of any question of conflict of interest, standards used by NIH in determining conflict of interest for advisory committee members and investigators shall apply.
- Members should assess trial objectives and design in an unbiased way.
- Members are guided both by pre-specified study performance criteria, such as early stopping rules, and also by a masked and, if necessary, unmasked review of all data prior to making decisions
- The DSMB members will review data and pertinent procedures in order to be confident that the data on which the decisions are based are accurate and complete.
- All decisions of the DSMB shall be independent

## PROTOCOL REVIEW AND DATA MONITORING

### Monitoring and Reporting Requirements

In collaboration with the Principal Investigator and study biostatistician, the DSMB will set data monitoring and reporting requirements before study enrollment begins. Members will review the interim analysis plan to ensure the analyses planned will provide necessary information for DSMB decisions. Members will participate in specification and review of all tables and specifications for data that they will review in accordance with timelines established by agreement with the Principal Investigator.

The DSMB will have face-to-face meeting(s) to review and discuss results of interim analysis. The DSMB may also have face-to-face meeting(s) as prompted by unplanned interim analyses deemed necessary because of safety concerns. The DSMB staff or chair will prepare minutes of each meeting within ten (10) working days of each meeting. These minutes will be circulated and approved at the next regularly scheduled meeting of the DSMB.

The Principal Investigator and study biostatistician will work with the DSMB for appropriate preparation of reports to be viewed at DSMB meetings and resolution of questions arising during data analysis. If requested by the DSMB, the Principal Investigator will turn over to the chairperson of the DSMB evidence of validation of all computer programs used to generate reports and analyses for each DSMB meeting. The documents will be made part of the minutes of each meeting. All formal reports will be circulated to the DSMB members no later than one week prior to each DSMB meeting.

### Data Review by the DSMB

DSMB meetings will consist of an open and a closed session. The open session will provide a forum for exchange of information among DSMB members, Principal Investigator, and study biostatistician. During the open session, the Principal Investigator may present a brief summary report of the study progress, including enrollment rates, data collection, and data quality. There will be an opportunity for the Principal Investigator to ask advice from the DSMB on any matter concerning conduct of the trial.

Only members of the DSMB will attend the closed session. During this session, the DSMB will address issues regarding the following: 1) safety concerns, 2) efficacy concerns, 3) termination of the trial due to pre-specified stopping criteria, and 4) ethical concerns. The DSMB will be furnished with relevant information by the Principal Investigator to make these decisions. During this session the DSMB members may ask the Principal Investigator to provide them with data that is partially unmasked (i.e., treatment A or treatment B without revealing what treatment A and B represent) or completely unmasked (i.e., identify treatment group).

In addition to the open and closed sessions, the voting members of the DSMB may meet in an executive session at their discretion. The DSMB will:

- Review the protocol and any protocol amendments
- Review the interim analysis monitoring plan, make recommendations, and give approval
- Review interim analysis reports and meet as a group
- Communicate recommendations in writing to the Principal Investigator

If there are any concerns about reviewed material (such as safety, efficacy, ethics, and stopping rules), the DSMB will take appropriate action. This may involve a request for additional information, or a request for an early, unscheduled meeting of the DSMB with the Principal Investigator and study biostatistician. At each meeting that includes review of interim data, the DSMB will recommend one of the following actions to the Principal Investigator, Biomedical IRB, and when appropriate the NC TraCS Institute Director or designated representative.

- Continue the study according to the protocol.
- Modify the study protocol. Modifications may include such items as changes in the inclusion/exclusion criteria, nature and frequency of safety monitoring, study procedures, study drug/intervention dosing, consent form changes, subject re-notification, and any other changes deemed necessary.
- Discontinue one or more study arms.
- Discontinue the study.

The DSMB may request additional data, analyses, or meetings to address specific concerns. The DSMB may hold additional meetings without knowledge of the sponsor or Principal Investigator.

### **Release of DSMB Recommendations**

The DSMB will refrain from revealing to the sponsor, Principal Investigator, or any other party information that would lead to compromising the integrity of the trial unless such a release is required to protect subject safety. In particular, the following guidelines will be followed with respect to the dissemination of the DSMB interim analysis results.

- Individual patient treatment assignments will not be revealed
- Individual center results will not be revealed
- The magnitude of treatment differences in efficacy will not be revealed
- Study results will not be communicated to investigators
- The DSMB will not make any public disclosures of its discussions and decisions
- The DSMB will complete a brief report documenting decisions and rationale behind its decisions. The report will be conveyed confidentially to the Principal Investigator and sponsor, who in turn, will forward it to appropriate regulatory agencies. A copy of the report will also be made available to the UNC Biomedical Institutional Review Board, in form that does not contain information that could compromise the integrity of the clinical trial.
- When appropriate a copy of the report will also be made available to the Director of the Lineberger Cancer Center and/or the Director of the Clinical Translational Research Center.
- All DSMB decisions will be deemed advisory to the Principal Investigator, UNC Biomedical Institutional Review Board, and the Director, NC TraCS Institute.

## APPENDIX C: Script for patient scheduled monitoring calls

Days 15, 30, 45, etc.

"Hello,

This call is to check on how you are feeling and assess whether your vasculitis remains inactive

I will ask you a few questions about symptoms you may feel that could suggest the vasculitis is active or that you may have an infection. In answering, please think about the period of time since your last visit with Dr xxx. If you have any of these symptoms, please also tell me if this is new (in the last 2 weeks, or older) and how severe it is (mild, moderate or severe)"

- 1- Fever
- 2- Ear pain or change in hearing
- 3- Red or painful eyes
- 4- Bleeding from the nose, or sinus pain
- 5- Hoarseness, "air hunger", difficulty taking a deep breath
- 6- Cough or shortness of breath
  - a. If cough, does anything come out? What color? Any blood in the sputum?
  - b. If shortness of breath: is it with exertion (with walking, doing house chores or going up stairs for example), or even at rest? Is it worse at night? Do you feel that you get short of breath more easily than before?
- 7- Chest pain.
  - a. How often, is it on exertion or even at rest? How long does it last? Does it change with position?
- 8- Any nausea or vomiting? How many times did you vomit? Was there any blood in it? When was the last time you vomited? Are you able to eat and keep your food down?
- 9- Any abdominal (belly) pain or diarrhea? Constipation?
  - a. If diarrhea: are the stool soft, black and smelly? Is there any blood in the stool?
- 10- Any joint pain? Are the painful joints red, hot or swollen? How long do they last?
- 11- Any rash? If yes, where is it? Is it on both sides of the body or only one side?
  - a. Is it painful?
  - b. Any open sores
- 12- Any unusual headaches? Is it severe (cannot function)? Is it unusual for you?
- 13- Any new numbness, tingling or weakness in any limb (arms, legs, fingers, toes)?

14- Is there anything else you are concerned about that I did not ask you about?

If any of the above are answered positively:

“Have you called your doctor or the study doctor about this?”

- If yes: “what did the doctor tell you it was?
  - Did she/he prescribe any new medication? Any other change in medication?
  - Do you feel better since?”
- If no: I will relay this to the study doctor and he/she will get back with you and/or see you in clinic in the next 2-3 days.

If none of the questions are answered positively:

“I just want to remind you that your next appointment is on xxx at xxx time. Please remember to call us at [name] to let us know if you are not feeling well between now and your next appointment. If it is after hours call the hospital operator and ask for the kidney doctor on call. Would you like me to remind you off the numbers to call?”

If yes: study doctor # [contact]; Study coordinator: [contact]; hospital operator: [contact]

Thank you for your time.”

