### **6.1. Subjects randomized to NO-maintenance therapy: the WATCH group**

The subjects randomized to no-treatment will be followed up very closely:

Subjects will have study visits every 4 weeks for the first four months and then every 6 weeks for a total of 24 months of follow-up from randomization. The first visit after randomization will be Visit 1. Visit 1 will be scheduled as soon as possible after randomization.

Subjects will be called by phone by a study coordinator, nurse or physician between each clinic visit for a review of their clinical history to detect any symptoms or signs suggestive of relapse of vasculitis. Should the patient report a symptom or sign suggestive of relapse, she/he will be seen in clinic within the following week for full evaluation. The phone call will be done about 14 days after the clinic visit for the first four months and about 3 weeks after the clinic visit once the subject is followed every 6 weeks. The phone call will be done within a +/- 5 days window. Subject will be trained on the symptoms to watch for and instructed to call study team if such a symptom occurs, without waiting for study phone call or study visit.

Study visits will take place either in the UNC Kidney and Hypertension Clinic, at the Clinical and Translational Research center (CTR) or in the UNC Hospitals Infusion Clinic. Subjects will be examined by a nephrologist, either their regular nephrologist or a nephrologist who is a member of the study team. Study-specific procedures for each visit are outlined below.

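### In Appendix C, a WATCH patient's symptom report goes to the study doctor only if the patient has not already called a doctor, an exception section 6.1 does not make

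*Combined protocol and SAP*

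**What the plan says.** Section 6.1 sets the rule for the WATCH arm. "Subjects will be called by phone by a study coordinator, nurse or physician between each clinic visit" to look for signs of relapse, and a patient who reports one "she/he will be seen in clinic within the following week for full evaluation". It states no exception for a patient who has already spoken to a doctor. Patients are also told to report symptoms themselves "without waiting for study phone call or study visit". Study visits are done by "either their regular nephrologist or a nephrologist who is a member of the study team".

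Appendix C gives the words for the call. After a positive answer the caller asks "Have you called your doctor or the study doctor about this". On a no, the caller says that the study doctor will be told and will call back or see the patient in 2 to 3 days. On a yes, the caller asks what the doctor said, whether medication changed, and finally "Do you feel better since". That branch stops there. The closing reminder of the next appointment and whom to call is given only when every answer is negative.

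On timing, section 6.1 sets the call at about 14 days after each visit in the first four months, then "about 3 weeks after the clinic visit once the subject is followed every 6 weeks", each within 5 days either way. Appendix C is headed "Days 15, 30, 45, etc". The WATCH schedule table has a call row only for 14 days after the monthly visits. Section 6.3.1 says that calls continue between visits but places the change to 6-weekly visits after week 64, although the visits it lists are 6-weekly from week 16.

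**The concern.** The calls are the scheduled check for relapse between visits in patients who are off immunosuppression. Time to relapse is both the primary endpoint (section 3.2) and the primary safety endpoint (section 3.4). Close follow-up is part of the ethical case for randomizing to no therapy (section 11, item 3), and every 2 new relapses in this arm prompt DSMB review (section 8.4).

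The script makes the relay depend on a question that does not bear on relapse risk. Having phoned a doctor does not make a symptom less suggestive of vasculitis. The question accepts the patient's own doctor as well as the study doctor, so a call to a physician with no part in the trial is enough to end the branch. The person reading the script may be a coordinator or nurse. If that person does only what the script says, the section 6.1 visit is not triggered, and the next BVAS may wait for the next scheduled visit.

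**Working it through.** **Rule against script**

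| Patient's situation | Section 6.1 | Appendix C |
|---|---|---|
| Suggestive symptom, no doctor called | Clinic visit within 7 days | Relay; call-back and/or visit in 2 to 3 days |
| Suggestive symptom, study doctor called | Clinic visit within 7 days | Follow-up questions; no relay, no visit |
| Suggestive symptom, only an outside doctor called | Clinic visit within 7 days | Follow-up questions; no relay, no visit |

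In the second row the study doctor already knows of the symptom, so the missing relay matters little. The third row is the exposed case.

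**Possible delay if a report is not triaged**

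The plan gives no figure to reproduce. The inputs are the visit spacing and call timing in section 6.1, the visit window of one week either way in section 6.3.1, and the 7-day standard in section 6.1. It is assumed that the call is timed from the actual date of the preceding visit and that nothing brings the next visit forward.

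Days beyond the standard = (gap between visits − day of call) − 7, with negative values set to 0.

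6-weekly phase, call on day 21 ± 5 = days 16 to 26:
- Nominal gap of 42 days: 42 − 26 − 7 = 9, to 42 − 16 − 7 = 19.
- Both visits varying by 7 days, gap 28 to 56: 28 − 26 − 7 = −5, so 0, to 56 − 16 − 7 = 33.

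4-weekly phase, call on day 14 ± 5 = days 9 to 19:
- Nominal gap of 28 days: 28 − 19 − 7 = 2, to 28 − 9 − 7 = 12.
- Both visits varying by 7 days, gap 14 to 42: 14 − 19 − 7 = −12, so 0, to 42 − 9 − 7 = 26.

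| Phase | Nominal dates | Both visits ± 1 week |
|---|---|---|
| 6-weekly | 9 to 19 days | 0 to 33 days |
| 4-weekly | 2 to 12 days | 0 to 26 days |

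**Call timing**

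Visits at weeks 0, 4, 8, 12 and 16 and then every 6 weeks to week 106 make 20 visits and 19 gaps: 4 of four weeks and 15 of six weeks. Section 6.1 therefore implies 19 calls, of which 15 (15/19 = 79%) fall after week 16 and have no row in the WATCH table. Carrying the Appendix C heading forward every 15 days to week 106 (day 742), which is an assumption, gives 49 dates (742/15 = 49.5, rounded down). The two schedules differ, but the script's is the denser one.

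**The case against.** The best reply is that a script is what the caller says to the patient, not the rule for what staff then do. Section 6.1 orders the visit, and silence in one branch does not cancel it. The yes branch also collects what a study doctor would need for triage: the diagnosis given, any change in medication, and the response.

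There are other safeguards. A new or worsening symptom is an adverse event (section 8.1). Adverse events are to be sought at every contact and recorded at once (section 8.2), and reviewed as they occur and monthly by the principal investigator (section 8.3). A need for more prednisone or for combined immunosuppressants counts as relapse (section 5.5). Outside records are to be obtained (section 7.2). The blinded reviewer works from history and laboratory data as well as BVAS (section 8.4). Appendix D lists a phone call template whose content is not shown and which may already contain a relay. The patient's doctor may well be the nephrologist who does the study visits.

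All of this stands, and it keeps the point small. It does not make the two texts agree. The relay is written into one branch and left out of the other, and monthly review cannot ensure a visit within 7 days.

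A reader might infer that relapses would be missed or that the primary endpoint is compromised. The documents do not support that: an untriaged report needs several stated procedures to fail together, and what is then at risk is a late in-clinic assessment rather than loss of the event. A reader might also infer from the timing mismatch that WATCH patients would be called too seldom. That does not follow either. Taken literally, the heading gives 49 calls against 19, and the table's silence on the 6-weekly phase is an omission, since section 6.3.1 says the calls continue.

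**Conclusion.** The concern holds as a minor inconsistency with a safety aspect. The Appendix C script does not carry the section 6.1 rule for a patient who has already called a doctor, and the exposed group is patients who called only a doctor outside the study. The size of that group cannot be estimated from the documents.

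The delays in the table are conditional: they describe a report that nobody in the study triages, and they are not expected delays. In the 6-weekly phase, the lower end reaches zero only when both visit windows are allowed to vary. The call-date heading, the missing table row and the week 64 sentence are drafting errors. None of them changes the design, the endpoint or the analysis.

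**What to change.** Take section 6.1 as the standard.

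1. In Appendix C, and in the phone call template if it repeats the script, have the caller state after any positive answer, whichever doctor was called, that the report will be passed to the study doctor. The study doctor decides whether it suggests relapse and, if so, sees the patient in clinic with a BVAS within 7 days. The 2-to-3-day call-back can stay as triage but does not replace that visit.
2. For consistency only: replace the Appendix C day heading with the section 6.1 timing (14 ± 5 days after the visits at weeks 0, 4, 8 and 12; 21 ± 5 days after the visits at weeks 16 to 100), add the 3-week call to the WATCH table, and change week 64 to week 16 in the section 6.3.1 sentence on visit frequency.

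The cost is one script line, one heading, one table row and one clerical correction. No visits or calls are added beyond those section 6.1 already requires. The downside is a relay and a short triage record for each positive call, including calls about symptoms that turn out not to suggest relapse.
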